7. SUBJECT DISPOSITION

The subjects that were randomized, completed the study PP and the ITT will be summarized in a table indicating the frequency number and percentage. A CONSORT diagram will be included to observe the availability of subjects in the study.

PROTOCOL DISCONTINUATIONS

The number of subjects and their percentage will be included in the table that includes those subjects that were excluded due to lack of compliance to the requested criteria in the protocol. It is important to identify the subjects that did not conclude the study before the definition of populations to study. Discontinuations to the protocol include: Adverse Events leading to discontinuation, failure to meet inclusion/exclusion criteria, failure to comply with the treatment, failure to comply with the visits, concomitant medication, medical contraindication, voluntary withdrawal of the subjects, death, or others.

8. DEMOGRAPHY AND POPULATION CHARACTERISTICS

Baseline characteristics and demographics will be summarized for PP and ITT population defined in section 2.3.1

Categorical variables will be summarized in tables of frequencies and percentages. Continuous variables will be described by mean, standard deviation, median, max and min.

They will be compared by treatment. For continuous variables a variance analysis (ANOVA) will be used for means comparison for independent samples. Categorical variables will be compared through the test of χ^2 Cochran-Mantel-Haenszel.

Demographic characteristics included age (years), race, weight, height and Body Mass Index (BMI).

MEDICAL HISTORY

The medical history refers to whether the subject presents or presented any relevant conditions (Yes/No), a summary of conditions, diseases or surgical procedures and if these are still active or not. The data will be summarized in tables of frequencies and percentages based on the total number of subjects included in each treatment group and will only be handled for informatory purposes.

PHYSICAL EXAM

The physical exam includes examining body parts such as the abdomen, gallbladder, cardiovascular, endocrine, gastrointestinal and immune system, muscle-skeletal, neurological, psychiatric, respiratory, limbs, head, nose, eyes, ears, lymph nodes and allergies, nutritional facts, scars, skin, thyroid, etc. This will be evaluated in detail at baseline and documented in each visit just if there exist clinical relevance. The information will be summarized in tables of frequencies and percentages based on the total number of subjects in each treatment group and will only be handled for informatory purposes.

VITAL SIGNS

Vital signs consider values of systolic and diastolic blood pressure, heart rate, pulse and temperature. These shall be reviewed as part of the physical examination and the information will be presented in every visit. The information will be summarized in tables with number of participating subjects (n), mean, standard deviation (SD), median, max and min and will only be handled for informatory purposes.

GYNECOLOGICAL EXAM

The gynecological exam includes examination of breasts, external genitalia, vagina, cervix, uterus, other abnormalities, etc. The information will be summarized in tables of frequencies and percentages based on the total number of subjects in each treatment group and will only be handled for informatory purposes.

OBSTETRIC HISTORY

This item considers the history of childbirth in pregnancy, such as premature labor or rupture of membrane, before 35 weeks in preceding pregnancy, with viable fetus. The information will be summarized in tables of frequencies and percentages based on the total number of subjects in each treatment group and will only be handled for informatory purposes.

PREBIRTH CONTROL

This control considers the obstetric formula (GPA), the date of the last normal menstruation and gestational age in accordance with the Date of Last Normal Menstruation (DLNM) and gestational age though Transvaginal Ultrasound in weeks. The obstetric formula will be summarized in tables of frequencies and percentages determined within each group and the gestational ages in the tables with the number of participating subjects (n), mean, standard deviation (SD), median, max and min, and will only be handled for informatory purposes.

LABORATORIES

To be done only at baseline and blood and urine samples will be taken.

INCLUSION AND EXCLUSION CRITERIA

These will be summarized according to the compliance of them. The information will be summarized in tables with frequencies and percentages according to the total number of subjects included in each treatment group and will only be handled for informatory purposes.

9. TREATMENT COMPLIANCE

For Group A, at the start of each visit, it will be recorded the number of capsules dispensed at the previous visit and the number of capsules used, the treatment compliance will be estimated in percentage. The compliance should be between 80 and 120% for each patient.

For groups B and C, it will only be recorded if removal of the pessary was necessary. In this case the subject will be early terminated from the study and the reason for discontinuation will be recorded.

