5.4.3. After insertion of the pessary or beginning of the administration with vaginal progesterone capsules and until 28 weeks of gestation, participants in the 3 treatment groups will be monitored every 4 weeks at the most or more often, if the site has established so as a control standard. After 28 weeks, patients should be monitored every 2 weeks. At every control visit, procedures applicable to their prenatal control and a transvaginal ultrasound by standard technique will be performed (patients receiving vaginal capsules), if considered necessary by the physician, or transvaginal using the technique recently described (25) (in patients with medicated pessary) to measure and record cervical length. The occurrence of possible side effects, adherence to treatment, and visits or hospitalizations due to threat or preterm labor will also be recorded, as well as the existence of potential causes for *ex-post* exclusion from the study. In addition, concomitant medication will be recorded at each visit.

5.4.4 Management of participants consulting due to a threat or premature labor will be conducted according to the diagnostic and therapeutic guidelines of the Ministry of Health (MINSAL) (Clinical Guide for Preventing Preterm Birth - MINSAL 2010) and the respective hospital's Obstetrics and Gynecology Service. In these cases, the treating physician will be provided with information about the progesterone treatment the patient is receiving in the study, and the decision for her continuation in the clinical study will be made jointly as far as possible, since the opinion of the treating physician shall predominate.

5.4.5 Every case will be closed at 36 6/7 weeks of gestation, or at the time of preterm birth. Data on the birth, condition at birth, and evolution of infants born preterm will be analyzed, recording morbidity and mortality through the time of discharge from the hospital.

The participant's attending health team (physicians and midwives) will be informed in writing about the participation of these women in the study by means of an identification

card that will be given to every woman participating in the study. In the pregnancy card, participation of these subjects in the study will be emphasized by means of a self-adhesive sticker detailing their participation in one of the treatment groups (pessary or capsule) and recorded in the medical history.

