#### 5.5. Placement and repositioning of the cerclage pessary containing sustained-release progesterone

Once the cervix length and positioning have been examined by transvaginal ultrasound, and any vaginal infection has been ruled out or treated, the progesterone pessary should be implanted by a professional qualified and trained for that purpose. For placement, the participant must be lying in supine position.

The removal of the pessary will be done by vaginal examination at week 36 6/7 or earlier, if there is any medical indication for induction of premature labor or elective cesarean section. The pessary will also be removed from participants in preterm birth labor not responding to treatment with tocolytics.

During controls or visits to emergency departments or medical offices, participants who report vaginal discharge should be examined by a physician to rule out infection by relevant testing (vaginal discharge smears for PCR), and deliver the appropriate treatment without the need to remove the pessary. This condition will be considered an adverse event.

In the event that the medicated cerclage pessary is spontaneously expelled it, will be repositioned within maximum 72 hours; if this does not occur, the patient will be withdrawn from the study but considered in the final statistical analysis under the intention-to-treat principle.

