#### 5.7. Study participant withdrawal

The progesterone cerclage pessary will be removed if the patient requests so, or if there is any adverse event not responding to treatment alternatives such as pathological vaginal discharge non-responsive to antibiotic therapy. These participants will not be replaced and the information collected from them will be included in the analysis since this is based on the intention-to-treat principle.

Follow-up of subjects withdrawn from the investigational product will be the same as the standard follow-up.

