## 5.8. Recording, quality control, and data management

Information about the characteristics of the participants, including demographics (race, age, parity, measures for calculation of body mass index [BMI]), and the medical and obstetrical records will be obtained directly from the participants and recorded in the study file. Information about the outcome of the pregnancy will be obtained from the hospital's medical records file or treating physician. Medical records of participants experiencing preterm birth labor before weeks 32 and 34 will be reviewed to determine the cause and establish whether the delivery was because of medical indication or spontaneous. Spontaneous deliveries will include those with prior preterm labor and those with rupture of membranes before the onset of labor. Quality control for screening, information management, and monitoring of adherence to protocol across the four sites will be performed regularly by the clinical study monitor.

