6. POPULATION DEFINITIONS

In order to meet the needs of the sub-groups of the Protocol, the following population sub-groups are defined:

Per Protocol (PP): It is defined as the subset of participants who meet the criteria of selection, who expressed their desire to participate in the study, who signed the informed consent form, that the drug has been administered to them and have completed all the visits required or till the termination of the pregnancy as per Protocol.

Intention to treat (ITT): It is defined as the subset of participants who meet the selection criteria, showing their desire to participate in the study, who signed the informed consent form, that the drug has been administered to them, who have at least completed the initial visit and at least one of the subsequent visits to the pessary referred to in the Protocol.

The main efficacy analysis will be carried out with a focus Per Protocol (PP), however it will also be carried out per Intention to Treat (ITT) all the analysis. Otherwise, the main safety analysis will be completed as ITT.

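### SAP section 9 ends study participation after a necessary pessary removal, with no exception for labour, so spontaneous births in the pessary arms could be classed as discontinuations and left out of the main per-protocol analysis

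*SAP*

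**What the plan says.** **SAP section 9 (Treatment compliance).** For the two pessary groups: "For groups B and C, it will only be recorded if removal of the pessary was necessary". The next sentence gives the consequence: "In this case the subject will be early terminated from the study and the reason for discontinuation will be recorded". The section neither sets apart removal for labour or delivery nor says that the delivery outcome is still collected.

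**Protocol 5.5.** The pessary comes out at 36 6/7 weeks, or earlier for an indicated induction or elective caesarean. In addition: "The pessary will also be removed from participants in preterm birth labor not responding to treatment with tocolytics". A woman with an unreplaced expulsion is withdrawn but kept in the final analysis under intention to treat.

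**Protocol 5.6.** A capsule user with adherence below 80%, or a gap of more than 72 hours, is likewise withdrawn but kept in the final analysis.

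**Protocol 5.7.** On removal at the woman's request or for an unresolved adverse event: "These participants will not be replaced and the information collected from them will be included in the analysis", under intention to treat. Also: "Follow-up of subjects withdrawn from the investigational product will be the same as the standard follow-up".

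**Protocol 5.4.5 and 5.8.** "Every case will be closed at 36 6/7 weeks of gestation, or at the time of preterm birth". "Information about the outcome of the pregnancy will be obtained from the hospital's medical records file or treating physician".

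**SAP sections 6 and 7.** The main efficacy analysis is per protocol (PP), and everything is repeated under ITT. PP requires all visits, or participation to the end of the pregnancy. ITT requires the initial visit and at least one later one. Section 7 wants women who did not conclude the study identified before the populations are defined.

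**The concern.** Protocol 5.5 makes failed tocolysis in preterm labour a reason for removal. That is the immediate precursor of a spontaneous preterm birth, the event being counted. Read literally, SAP section 9 then labels the woman as terminated early because the event is happening to her. Labour triggers no such automatic label in the capsule arm, which has no device to remove.

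If the label is carried into section 7 and from there into the PP set, the births that leave the analysis are selected by outcome and come from the pessary arms. The apparent pessary rate falls even if the treatments are equally effective. The trial is open-label, so whoever assigns the label knows the arm.

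**Working it through.** **1. One woman, four rules.** Take a woman in group B or C whose tocolysis fails, whose pessary is removed and who then delivers spontaneously before 34 weeks.

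| Source | How she is treated |
|---|---|
| SAP 9 | Removal was necessary: terminated early from the study |
| SAP 7 | Fits the description of a woman who did not conclude, to be identified before populations are set |
| SAP 6, PP definition | Participated to the end of pregnancy: can be kept |
| Protocol 5.4.5 and 5.8 | Case closes at the preterm birth; outcome taken from hospital records or the treating physician |

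The SAP gives two answers and no text in it chooses between them. Its ITT set does not cover every case: a woman whose pessary is removed before any second visit fails the ITT definition too, and section 5 leaves baseline-only subjects out of the tables.

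**2. Inputs for an illustration.** The plan has no figure of its own for this loss to reproduce. From the documents: 90 women per group, two-sided alpha 0.05, uncorrected chi-square (Protocol 9.1). Assumed, because the documents give neither: the true risk p, equal in both arms, and the share f of pessary-arm events left out. The comparison is one pessary arm against capsules.

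**3. Formulas.** Events kept in the pessary arm: 90p(1−f). Women kept: 90 − 90pf. Apparent rate: q = p(1−f)/(1−pf). The odds become (1−f)·p/(1−p), so the expected odds ratio is 1−f although the true one is 1.

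**4. One case by hand: p = 20%, f = 50%.**
- Capsules: 18/90 = 20.0%. Pessary: 9/81 = 11.1%. Difference d = 0.0889.
- Pooled rate: 27/171 = 0.158. Null standard error: √(0.158 × 0.842 × (1/90 + 1/81)) = 0.0558.
- Standard error at the apparent rates: √(0.20 × 0.80/90 + 0.111 × 0.889/81) = 0.0547.
- Rejection probability ≈ Φ((0.0889 − 1.96 × 0.0558)/0.0547) = Φ(−0.375) ≈ 0.35. The other tail is negligible.

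Simulation gives about 36%.

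**5. Range.** Each cell shows the apparent pessary rate, then the simulated chance that the nominal 5% test rejects (at least 200,000 trials per scenario; 33% is taken as one third).

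| True risk | 20% lost | 33% lost | 50% lost |
|---|---|---|---|
| 5% | 4.0%; about 5% | 3.4%; about 7% | 2.6%; about 12% |
| 15% | 12.4%; about 8% | 10.5%; about 14% | 8.1%; about 29% |
| 20% | 16.7%; about 9% | 14.3%; about 17% | 11.1%; about 36% |
| 30% | 25.5%; about 10% | 22.2%; about 21% | 17.6%; about 46% |

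At 20% risk, about 93%, 99% and over 99% of the rejections favour the pessary. With only 10% of events lost at that risk, rejection is about 6%. With none lost there is no bias.

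The low-risk row matters because SAP section 10 counts only births after 32 and before 34 weeks. In so short a window, 20% may be far too high.

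**The case against.** The strongest reply is that leaving the study does not mean leaving the analysis in these documents. Protocol 5.5 and 5.6 both withdraw a woman and still analyse her. SAP section 9 concerns compliance and excludes no data. A woman who delivers after failed tocolysis fits the PP clause on reaching the end of pregnancy, birth is recorded at the final visit in every arm, all analyses are repeated under ITT, and SAP section 1 makes the protocol the final reference. All of this stands, and it is why loss cannot be called certain. It does not settle the matter: the SAP omits the protocol's statement that such women are still analysed, and the literal wording of sections 7 and 9 points the other way.

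A reader might also infer that women can be lost from the pessary arms only, and that every corresponding capsule birth stays. The documents do not support that. Capsule users can be withdrawn for non-adherence (Protocol 5.6; SAP section 7). Under Protocol 5.4.4, continuation after threatened or premature labour is decided case by case in all three arms. What is particular to the pessary groups is the automatic rule.

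Nor does every removal trigger it. The SAP speaks of removal that was necessary, and planned removal at 36 6/7 weeks is not the natural reading of that. Finally, the bias need not run one way for all removals: leaving out a woman without the event shrinks only the denominator and raises the pessary rate. The tilt towards the pessary belongs to removals prompted by labour.

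**Conclusion.** The point holds as a conflict between stated rules that bears on who is counted in the main efficacy comparison. SAP section 9 lets the primary event in progress trigger termination in groups B and C. That is at odds with Protocol 5.7 on follow-up and analysis after the product is stopped, and with the SAP's own PP definition.

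It does not show that births will be lost or that the result will be biased. A reader might take the 36% above as the trial's false-positive rate. It is not: it needs an assumed 20% risk and half of all pessary-arm events dropped. Under the assumptions shown, the inflation runs from negligible (about 5% at 5% risk with 20% lost) to large (about 36% at 20% risk and 46% at 30% risk, with half lost). If the PP clause is applied so that these women are kept, it is nil.

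This should be fixed before the populations are defined, because in an open-label trial the choice should not be left until outcomes are known. It falls short of a demonstrated flaw in the primary result.

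**What to change.** In SAP section 9, replace the early-termination sentence with text to this effect:

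- Pessary removal is recorded, with date and reason, as discontinuation of the product only.
- Date and type of delivery are collected for every randomised woman in all three arms, to delivery or 36 6/7 weeks.
- She is analysed in her randomised arm under ITT. The ITT definition in section 6 should not drop her because removal came before a second visit.
- Removal because of labour or for delivery is not a discontinuation and does not exclude her from the PP set.

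Unreplaced expulsion and capsule non-adherence need separate wording. Protocol 5.5 and 5.6 withdraw these women but keep them in the final analysis, so a SAP sentence saying that they stay in the study would create a new contradiction. The SAP should say instead that their delivery outcome is still collected and analysed.

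The cost is SAP wording. Delivery outcomes already come from hospital records or the treating physician, so no visit or procedure is added and no clinical rule changes. A protocol amendment would arise only if the sponsor wished to change the withdrawal status set in Protocol 5.5 or 5.6.

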10. EFFICACY ANALYSIS

STATISTICAL HYPOTHESIS

Null Hypothesis:

There is no difference between the methods of cerclage pessaries with a sustained release of 6.3 and 7.7 g of progesterone (Treatments B and C, respectively) with respect to the control method (Treatment A) for at least 20 weeks.

Alternative Hypothesis:

There is a difference between the Control Method (Treatment A) with respect to the one of cerclage pessaries with a sustained release of 6.3 and 7.3 of progesterone for a period of 4 to 5 months.

“There is a difference between the methods of cerclage pessaries with a sustained release of 6.3 and 7.3 g of progesterone (Treatments B and C respectively) with respect to the Control Method (Treatment A) for a period of 4 to 5 months”.

PRIMARY ANALYSIS

The primary objective is to evaluate the efficacy of two cerclage pessaries with doses of 6.3 and 7.7 g of sustained release micronized progesterone with respect to the standard treatment of 200 mg of progesterone in capsules administered daily. The primary efficacy analysis will be assessed by comparing the proportions of spontaneous premature delivery after 32 weeks but before 34 weeks of gestation, as primary results, among treatments through the CMH test. Also, the odds ratio and 95% confidence interval will be estimated, considering Group A as the control to be compared with groups B and C. Secondly, the comparison of proportions between the groups C and A will be done with the intention to confirm the significant difference between the highest dose and the standard treatment. Afterwards, the same comparison of proportions will be done with treatment B in order to establish the difference between the group of a minor dose and the standard. Finally the comparison between treatment B and C will be done hoping to demonstrate there is a difference of superiority between B and C where C must be minor than B regarding the number of low-risk pregnancies. The transitivity between treatments will be established according to the results. This is expected to be as follows:

$$\textit{Treatment C} < \textit{Treatment B} < \textit{Treatment A}$$

this is in terms of decrease of the proportion of pregnancies with premature risk. In this way it will be determined the effective response to progesterone in the cerclage pessary through the occurrence of spontaneous delivery after 32 weeks but before 34 weeks of gestation. The evaluation of the error type 1 will be with a value of 0.05 for the type of variable being used.

As part of the exploratory analysis for the efficacy of treatments, the risk of spontaneous premature birth from the moment of inclusion in the study until the weeks 32 and 34 of gestation, will be determined with the Kaplan-Meier analysis, where the gestational age is the timeline, spontaneous delivery will be the event and elective deliveries will be censored. A singleton pregnant subject between 16 and 24 weeks of gestation will be eligible to participate in the study when she meets one of the following two conditions:

- Cervical length between 10 to 25 mm and without risk factors
- Cervical length greater or equal to 10 mm and with pre-existing risk factors in the immediate preceding pregnancy characterized by:
 - premature delivery before the week 35 (with a viable fetus)
 - premature rupture of membrane prior to week 35 (with a viable fetus)

There are two ways to measure the gestational age which are the following:

- Gestational Age according to DLNM (weeks)
- Gestational Age according to Transvaginal Ultrasound (weeks)

The time of gestational age will be evaluated through log-rank tests among treatments. The null hypothesis is stated as the no treatment differences in the gestational ages.

Kaplan-Meier (product limit) estimates of the gestational age distribution will be calculated and their corresponding 95% confidence interval (CI) will be presented: 25th percentile, mean, median, and 75th percentile.

The analysis will be performed for the two measurements of gestational time, considering the Transvaginal ultrasound the one most accurate.

For the purposes of this analysis, pregnancies will no longer be considered of high risk in the event birth takes place in week 34 (34 0/7) of gestation or more.

SECONDARY ANALYSIS

For some of the secondary variables, subjects will be their own controls in the following variables to evaluate and the following analysis are proposed:

Occurrence of membranes' ruptures: Premature rupture of membranes after 32 weeks but before 34 weeks of gestation. The Cochran-Mantel-Haenszel (CMH) test will be used, where the incidence of rupture of membranes in each group will be compared and will be identified through the registration of adverse events.

Anatomical cervical changes (Only groups B and C): The length of the cervix and cervical angle variables, will be described as continuous and measured variables through time, using the test of comparison of means through the Analysis of Variance (ANOVA) for repeated measures, considering the baseline result as a covariate in the comparison and shall be based on the sum of squares type III. The difference between groups regarding the change from baseline will be assessed through t tests paired within ANOVA, utilizing the difference in means estimated by least squares. These comparisons will be made amongst all treatment groups with pessary.

Acceptability and tolerability of insertion (only groups B and C):

Acceptability and tolerability will be assessed through a questionnaire which must be completed at the beginning and end of the study. Questions (i) and (ii) are answered at visit 1, question iii (VAS) is answered at visit 1 and final visit, and questions (iv) to (ix) are answered at the final visit.

It is composed of several items

- (i) Ease of insertion (visit 1). This question has the following categories: 1 = very good, 2 = good, 3 = regular, 4 = bad and 5 = very bad; and only one of them will be selected.
- (ii) Subjects pain at the time of insertion (visit 1). This question has the following categories: 1 = without pain, 2 = with little pain, 3 = with moderate pain, 4 = with intense pain and 5 = with unbearable pain; and only one of them will be selected.

- (iii) Visual Analog Scale of pain (VAS) (visit 1 and final visit): this scale is evaluated in 10 points where 10 represents the worst pain suffered during her lifetime and 1 the absence of pain.

Analysis for the VAS will be described as continuous and measured variables through time using the test of comparison of means through the Analysis of Variance (ANOVA) and must be based on the sum of squares type III. The treatment differences regarding the change from baseline, will be assessed through t tests paired within ANOVA, utilizing the difference in means estimated by least squares. These comparisons will be made amongst all treatment groups.

- (iv) Expulsion of the Pessary (Yes/No, Final Visit). The date, gestational age of expulsion of the pessary without replacement will be recorded in the log.
- (v) Sensation upon the release of the pessary (Final visit). This question has the following categories: 1 = never, 2 = almost never, 3 = occasionally, 4 = frequently, 5 = always; and only one of them will be selected.
- (vi) Release of vaginal fluid (Final visit). This question has the following categories: 1 = never occurred, 2 = No changes, 3 = little increase, 4 = big increased 5 = change in color; and only one of them will be selected.
- (vii) Sexual intercourse with pessary (Final Visit). This question has the following categories: 1 = better, 2 = as always, 3 = with discomfort, 4 = with pain, 5 = no intercourse; and only one of them will be selected.
- (viii) Request for early withdrawal of the pessary (Yes/No, Final visit). The date, gestational age and reason of withdrawal from the pessary will be recorded in the log.
- (ix) Recommendation (Yes/No, Final Visit).

For all the above items except number (iii), the information will be summarized in the frequency and percentage tables according to the total number of subjects included in each treatment group and will be handled only for informatory purposes.

Changes in vaginal discharge

Clinical evaluation and/or bacteriological research will take place, infections will be treated with the appropriate antibiotic in case it is confirmed. For these cases, the insertion of a cerclage pessary with sustained-release of progesterone, will take place later at the end of the treatment, but before 24 (0/1) weeks of gestation. It will be monitored in each visit.

In each control, the participant will be asked about the presence, quantity and physical characteristics of the vaginal discharge. To discard presence or absence of infections, the subject will be asked about the need to do a smear of the vaginal discharge for PCR and the need for treatment. The information will be summarized in tables of frequencies and percentages based on the total number of subjects included in each treatment group per visit. A generalized CMH test will be used to assess whether changes in vaginal discharge were different in any of the groups through time.

Children Evaluation

New born will be described in the aspects of demography, physical exam (gestational age), cephalic perimeter, APGAR score, neonatal complications, medical interventions and discharge status. Summary tables of descriptive statistics, absolute and relative frequencies will be included in the analysis only as a descriptive purposes.

